## 7.5 Equipment

The following equipment will be provided by the sponsor to the sites:

Digital photography equipment

IAD Measurement Sheet

 3M Deutschland GmbH [name] [name], Germany	Clinical Investigational Plan / Protocol  3M Confidential	CLIN-PROT-EU-05-293312 Version: 3 Status: Release Release Date: 01/30/2018 07:29:52 AM CST Page 29 of 60
--	---	---

Stopwatch

Scale

#### **7.6 Replacement of patients**

Patients who discontinue before the first product application will be replaced with another patient.

### **8. Study device(s) and comparator(s)**

#### **8.1 Description of the exposure**

Cavilon Advanced Skin Protectant will be applied every 72 hours in this study.

The comparator products will be applied according to the local hospital IAD care intervals following the hospital medical routine.

#### **8.2 Number of study devices**

Cavilon Advanced Skin Protectant will be applied 7 times in maximum for a study period of 21 days. Sufficient amounts of applicators will be shipped to the study centers.

#### **8.3 Justification of the choice of comparator(s)**

The intention of the study is to assess the effects of Cavilon Advanced Skin Protectant in comparison to local hospital IAD standard care regime. In the comparator group the patients will be treated with the usual hospital IAD care products according to the medical routine of the hospital.

#### **8.4 Other medical device or medication**

Not applicable

#### **8.5 Regulatory requirements of study material**

3M™ Cavilon™ Advanced Skin Protectant is a CE-marked medical device class IIa according to the Medical Device Directive 93/42/EEC, Annex IX, rule 4.

 
3M Deutschland GmbH [name] [name], Germany
	
Clinical Investigational Plan / Protocol
 
3M Confidential
	
CLIN-PROT-EU-05-293312 Version: 3 Status: Release Release Date: 01/30/2018 07:29:52 AM CST Page 30 of 60

--	--	---

## 9. Patients

### 9.1 Inclusion criteria

Patients may be enrolled into this study if the answers to all these questions are yes.

1. Is the patient 18 years or older?
2. Has the patient or their legally authorized representative signed the Informed Consent Form?
3. Does the patient have IAD category 1A or IAD category 2A in the study area\*?
4. Is the patient incontinent and does stool and/or urine come into direct contact with the skin?
5. Is the patient able to be turned/positioned with regard to skin assessment and photo documentation?
6. Is there a reasonable expectation that the patient will remain in the hospital setting for at least 7 days?

\*NOTE: Study Area

The study area is defined as the sacral region going down to the upper thighs, bordered approximately 5 cm below the gluteal fold.

Study Area: IAD has to be present in this zone at the start of the study

### 9.2 Exclusion criteria

Patients are excluded from participation in this study if any of the answers to these questions are yes.

1. Is the patient pregnant or breast feeding?
2. Does the patient have a known hypersensitivity or allergy to acrylate or cyanoacrylate?
3. Does the patient have a stage II, III, IV or unstageable pressure ulcer or other suspected deep tissue injury in the study area?
4. Does the patient require topical treatment due to a fungal, bacterial or viral infection in the study area?
5. Does the patient require treatment with topical medication or product other than IAD treatment in the study area?

 3M Deutschland GmbH [name] [name], Germany	Clinical Investigational Plan / Protocol  3M Confidential	CLIN-PROT-EU-05-293312 Version: 3 Status: Release Release Date: 01/30/2018 07:29:52 AM CST Page 31 of 60
--	---	---

6. Does the patient have any other local dermatological disease or skin condition interfering with this study?
7. Does the patient have any medical condition (e.g. end of life, planned elective surgery) that in the opinion of the investigator should exclude him/her from participating in the study?
8. Does the patient participate in another study with a known or implied effect on skin barrier function?

### **9.3 Criteria and procedures for patient withdrawal or discontinuation**

The following withdrawal/discontinuation criteria are defined for the study:

1. Patient develops a stage III, IV or unstageable pressure ulcer or any other deep tissue injury in the study area.
2. Patient develops a fungal, bacterial or viral infection or other condition requiring the use of topical medication or product in the area treated with IAD products.
3. Patient develops any condition which, in the opinion of the Investigator, requires discontinuation from the study including pregnancy.

The date and reason for withdrawal/discontinuation will be documented in the “end of study” documentation and recorded as adverse event if applicable.

### **9.4 Point of enrolment**

The patient is enrolled for the study if the patient meets all inclusion and exclusion criteria and signed the informed consent form.

### **9.5 Total expected duration**

The total expected duration of the study is 10 months including an enrollment period of 9 months.

### **9.6 Expected duration of each patient’s participation**

The maximum duration of each patient’s participation is 21 days. If IAD heals before 21 days and the patient is still incontinent, the patient will stay in the study to assess IAD recurrence rate with continued application of the study device (Cavilon Advanced Skin Protectant) or in the case the patient is allocated to the local IAD care regime with products following the local

 
3M Deutschland GmbH [name] [name], Germany
	
Clinical Investigational Plan / Protocol
 
3M Confidential
	
CLIN-PROT-EU-05-293312 Version: 3 Status: Release Release Date: 01/30/2018 07:29:52 AM CST Page 32 of 60

--	--	---

IAD prevention regime. If IAD heals before 21 days and incontinence discontinued or incontinence constituents are not in direct contact with the skin anymore, the patient will be released from the study. Patients discharged from the hospital prior to 21 days fulfill the requirements for study completion and are not followed-up outside of the hospital. The maximum patient participation is 21 days. If IAD heals before 21 days and the patient is still incontinent, the patient will stay in the study in order to assess the IAD recurrence rate. The patient will continue treatment either with Cavilon Advanced Skin Protectant or the local IAD care regime depending on the assigned study arm. If IAD heals before 21 days and the patient is no longer incontinent (or incontinence constituents are not in direct contact with the skin anymore) the patient will be released from the study irrespective of allocation group. Patients that have completed at least 5 days, but terminate the study prior to 21 days i.e. due to hospital discharge, fulfill the requirements for study completion and are not followed-up outside of the hospital. Note: Any recurrence of IAD in both study groups is to be examined. If the hospital routinely does not use IAD prevention products, the recurrence of IAD is still to be observed for the group allocated to standard care. In this case, the study procedures of “Application: Comparator” and “Pain Score: Application” no longer apply (Appendix 24.1 B).

**9.7 Number of patients required**

Due to the exploratory design no formal a priori hypothesis is defined. The intention is to learn more about the effect size of certain variables such as healing outcome when compared to different local IAD care regimes in hospitals. The results of the study will be used to examine the feasibility of a potential subsequent confirmatory RCT.

Total: n = 60 patients

Stratum 1: n = 30 IAD 1A patients

(persistent redness without clinical signs of infection)

Stratum 2: n = 30 IAD 2A patients

(skin loss without clinical signs of infection)

The patients will be allocated 1:1 to either Cavilon Advanced Skin Protectant or hospital IAD standard care.

 3M Deutschland GmbH [name] [name], Germany	Clinical Investigational Plan / Protocol  3M Confidential	CLIN-PROT-EU-05-293312 Version: 3 Status: Release Release Date: 01/30/2018 07:29:52 AM CST Page 33 of 60
--	---	---

Each site is expected to recruit 10 IAD 1A and 10 IAD 2A patients:  
5 IAD 1A patients allocated to Cavilon Advanced Skin Protectant  
5 IAD 1A patients allocated to hospital IAD care  
5 IAD 2A patients allocated to Cavilon Advanced Skin Protectant  
5 IAD 2A patients allocated to hospital IAD care

**9.8 Enrolment period**

The enrollment period is expected to be 9 months.

**10. Treatment of patients**

The patients will be treated either with Cavilon Advanced Skin Protectant (study device) or IAD hospital standard care (comparator)

Treatment with Cavilon Advanced Skin Protectant

Cavilon Advanced Skin Protectant will be applied to the study area that is defined as the sacral region going down to the upper thighs, bordered approximately 5 cm below the gluteal fold (IAD affected as well as unaffected skin). The genital area and the frontal skin folds will be treated only in case of visible IAD and only for the IAD affected skin. In consideration of the manufacturer’s instruction for use no topical medication or other product shall be applied on top of the barrier film because the effectiveness of either film or medication might be reduced.

Application Cavilon Advanced Skin Protectant

Complete Area (Treatment/Prevention)

ONLY VISIBLE IAD (Treatment)

Treatment with IAD hospital standard care products

The hospital standard care products of the comparator group will be applied to the skin areas following the local hospital procedures and considering the manufacturers’ instructions for use especially with regard to contraindications. The use of topical medication or product other than the IAD treatment is not allowed for the study area in the comparator group.

 3M Deutschland GmbH [name] [name], Germany	Clinical Investigational Plan /  Protocol  3M Confidential	CLIN-PROT-EU-05-293312 Version: 3 Status: Release Release Date: 01/30/2018 07:29:52 AM CST Page 34 of 60
--	--	---

## 11. Assessment of effects/performance

### 11.1 Effect/performance parameters

Cavilon Advanced Skin Protectant in comparison to IAD Hospital Standard Care

IAD Healing/Improvement

- ✓ IAD severity category according to the Ghent Global IAD Categorization Tool [33] evaluated by the research study nurses on-site
  - IAD 1A: persistent redness without clinical signs of infection
  - IAD 1B: persistent redness with clinical signs of infection
  - IAD 2A: skin loss without clinical signs of infection
  - IAD 2B: skin loss with clinical signs of infection
  - IAD free: skin free of any IAD signs, including erythema
- ✓ IAD affected area in cm^2 evaluated by the research study nurses on-site
  - Total IAD affected area inclusive signs of erythema (measurement sheet estimate)
  - Area affected by IAD skin loss (measurement sheet estimate)
- ✓ IAD severity category according to the GLOBIAD Tool evaluated by the blinded assessor based on the photographs of the study area that is defined as the sacral region going down to the upper thighs, bordered approximately 5 cm below the gluteal fold.
  - IAD 1A: persistent redness without clinical signs of infection
  - IAD 1B: persistent redness with clinical signs of infection
  - IAD 2A: skin loss without clinical signs of infection
  - IAD 2B: skin loss with clinical signs of infection
  - IAD free: skin free of any IAD signs, including erythema
- ✓ IAD affected area in cm^2 traced by the blinded assessor based on the photographs of the study area.
  - Total IAD affected area inclusive signs of erythema (software calculation in cm^2)
  - Area affected by IAD skin loss (software calculation in cm^2)
- ✓ Time to healing in days
  - Number of days to achieve improvement in severity category according to the GLOBIAD Tool or days until complete healing without any signs of erythema

 
3M Deutschland GmbH [name] [name], Germany
	
Clinical Investigational Plan / Protocol
 
3M Confidential
	
CLIN-PROT-EU-05-293312 Version: 3 Status: Release Release Date: 01/30/2018 07:29:52 AM CST Page 35 of 60

--	--	---

Prevention of IAD Deterioration and Recurrence

- ✓ IAD severity category according to the Ghent Global IAD Categorization Tool evaluated by the research study nurses on-site and the blinded assessor based on the photographs of the study area.

Pain Assessment

(only for cognitively healthy patients according to the judgement of the study nurse)

- ✓ IAD pain scores according to the Wong-Baker FACES® Pain Rating Scale at the start and the end of the study (pain scores 0 – 10)
- ✓ Pain scores according to the Wong-Baker FACES® Pain Rating Scale associated with the incontinence cleanup (pain scores 0 – 10)
- ✓ Pain scores according to the Wong-Baker FACES® Pain Rating Scale associated with the IAD product application (pain scores 0 – 10)

Material cost and resource use

- ✓ Material cost based on the information with regard to the utilization of certain IAD care products such as cleansing products, skin protectants building up the moisture barrier, IAD wound dressings or other products, their used quantity, application frequency and duration of use.
- ✓ Resources involved in the IAD therapy (e.g. number of nurses or specialists/ number of interventions)

IAD Nursing Time

- ✓ Time taken to clean up incontinence in minutes
- ✓ Time taken to apply the skin protectant building up the moisture barrier and other products that might be needed to prepare the skin ( e.g. lotions to dry-out lesions before applying the skin protectant building up the moisture barrier)

**11.2 Assessment method**

Barthel Index [26]

The Barthel Index will be completed at the start of the study to characterize the patients with regard to their degree of independence in activities of daily living. The evaluation addresses 10 items: help needed with feeding, help needed with transfers e.g. from chair to bed, help needed with grooming, help needed with toilet use, help needed with bathing, help needed

 3M Deutschland GmbH [name] [name], Germany	Clinical Investigational Plan / Protocol  3M Confidential	CLIN-PROT-EU-05-293312 Version: 3 Status: Release Release Date: 01/30/2018 07:29:52 AM CST Page 36 of 60
--	---	---

with walking, help needed with climbing stairs, help needed with dressing, presence or absence of fecal incontinence and presence or absence of urinary incontinence. The possible scores range from 0 – 100, with lower score indicating increased disability.

Braden Scale for Predicting Pressure Sore Risk [29, 30]

The Braden Scale will be completed at the start of the study to assess the patient’s level of risk for development of pressure ulcers. The evaluation is based on six indicators: sensory perception, moisture, activity, mobility, nutrition, and friction or shear. Total possible scores range from 6-23, with lower score indicating a higher risk of developing a pressure ulcer.

Wong-Baker FACES® Pain Rating Scale [31]

This pain assessment tool was originally created with children for children to help them communicate about their pain. Faces with different expressions from smiling to crying facilitate the communication as anchor for pain intensity scale 0 – 10, with higher score indicating more pain. The nurses will ask the patients to choose the face that best depicts the pain they are experiencing. Only cognitively healthy patients according to the judgement of the study nurse will be asked. The IAD pain scores will be assessed before and during cleansing following the local hospital cleansing procedure. In addition the IAD pain scores will be measured before, during and after application of the skin protectant building up the moisture barrier.

Pain assessment instructions (not valid for patients with reduced consciousness or dementia)

1. Explain to the patient that each face represents a person who has no pain (hurt), or some, or a lot of pain

Figure 1: © 1983 Wong-Baker FACES Foundation. www.WongBakerFACES.org. Used with permission

3M Deutschland GmbH  
[name]  
[name], Germany

**Clinical Investigational Plan /  
Protocol**

**3M Confidential**

CLIN-PROT-EU-05-293312

Version: 3

Status: Release

Release Date: 01/30/2018

07:29:52 AM CST

Page 37 of 60

2. Face 0 doesn't hurt at all. Face 2 hurts just a little bit. Face 4 hurts a little bit more. Face 6 hurts even more. Face 8 hurts a whole lot. Face 10 hurts as much as you can imagine, although you don't have to be crying to have this worst pain.
3. Ask the patient to choose the face that best depicts the pain they are experiencing.

IAD Nursing Time

The time taken to clean up incontinence and to administer the IAD treatment products will be measured with a stopwatch at Day 04 (+/- 1 day) preferably in the presence of fecal constituents. Additionally, the skin protectant building up the moisture barrier will be weighed before and after application for those patients allocated to the usual IAD hospital care regime

Nursing Time Instructions:

Preparation:

1. Collect supplies and prepare the room
2. Familiarize with the sponsor provided stopwatch
3. Remove diapers/pads. Dispose coarse dirt that can be grabbed with a wipe.

Time to clean up incontinence (back side & front):

1. Timekeeper starts stopwatch when nurse indicates start of cleansing procedure with picking up the cleanser
2. Timekeeper stops stopwatch when nurse indicates cleansing procedure is complete (exclusive time to cleanup location)

Time to administer IAD treatment products:

Study area: Sacral region going down to the upper thighs, bordered approximately 5 cm below the gluteal fold.

1. Familiarize with the sponsor provided scale
2. Weigh the skin protectant building up the moisture barrier if the patient is allocated to the IAD hospital standard care group (content in gram before application)
3. Timekeeper starts stopwatch when nurse indicates start of application of IAD product(s) with product in hand (IAD product(s): skin protectant building up the moisture barrier and other products such as dry-out lotions to prepare the skin if needed)

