## 7.3 Endpoints

Due to the exploratory design of the study the endpoints are not divided into primary and secondary endpoints.

The following endpoints are defined for the study with regards to the comparison of Cavilon Advanced Skin Protectant and local IAD hospital care:

1. Number and percentage of patients completely healed (skin free of any IAD signs, including erythema)
2. Number and percentage of patients improved with regard to IAD category
3. Number and percentage of patients with 100% re-epithelialization of skin loss (skin loss: skin is moist, as the epidermal layer is missing)
4. Time to complete healing or reduction in IAD category
5. Protection of IAD category 1 patients from developing IAD category 2
6. Prevention with regard to IAD recurrence
7. Material cost based on product utilization such as type of products, frequency of application and days of treatment
8. Use of resources involved in the IAD therapy
9. Nursing time to clean up incontinence and to administer IAD treatment products
10. Pain scores with regard to cleansing procedure and application of IAD product (Wong-Baker FACES® Pain Rating Scale: assessment only for cognitively healthy patients according to the judgement of the study nurse)

 3M Deutschland GmbH [name] [name], Germany	Clinical Investigational Plan /  Protocol  3M Confidential	CLIN-PROT-EU-05-293312 Version: 3 Status: Release Release Date: 01/30/2018 07:29:52 AM CST Page 25 of 60
--	--	---

11. Number and percentage of patients with adverse events and the nature of each adverse event

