**Study Schedule: Day 02 – Day 20**

1. Perform skin cleansing
2. Day 04, Day 07, Day 10, Day 13, Day 16, Day 19, End of Study (discontinuation):  
Ask the patient to indicate the IAD pain level before and during cleansing using the Wong-Baker FACES® Pain Rating Scale (assessment only for cognitively healthy patients according to the judgement of the study nurse).
3. Day 04 IAD Nursing Time: Measure the time taken to clean up incontinence (front/back) and the time taken to administer the IAD treatment products to the study area that is defined as the sacral region going down to the upper thighs, bordered approximately 5 cm below the gluteal fold (patients assigned to Cavilon Advanced Skin Protectant and patients assigned to the local hospital IAD care regime). Please consider the nursing time measurement instructions (stopwatch and scale provided by the sponsor). Measure the

 3M Deutschland GmbH [name] [name], Germany	Clinical Investigational Plan /  Protocol  3M Confidential	CLIN-PROT-EU-05-293312 Version: 3 Status: Release Release Date: 01/30/2018 07:29:52 AM CST Page 27 of 60
--	--	---

weight of the skin protectant building up the moisture barrier before and after application if the patient is assigned to the local hospital IAD care regime group.

4. Perform a structured IAD skin assessment according to the GLOBIAD Tool. Estimate the IAD affected area in cm^2 using the measurement sheet provided by the sponsor (either of the total affected IAD area inclusive signs of erythema or with focus on skin loss only). Fill out the IAD study diary with regard to skin assessment information.
5. Photographs should be taken on Day 04, 07, 10, 13, 16, 19 and End of Study (Day 21 or discontinuation). Additional photos should also be taken at the first day no evidence of IAD is present (e.g. no erythema, no skin damage), i.e. transition from IAD1 to IAD free. If a patient has IAD 2 skin lesions/skin loss, additional photos should be taken on the first day of 100% re-epithelialization, i.e. IAD2 transition to IAD 1. Photographs must be taken according to the site procedure manual. Photos must be uploaded into the database if they refer to a study endpoint – either Day 01, Day 21, IAD2 to IAD1 or IAD1 to IAD free. Photos should be kept on the respective SD memory cards, labelled according to the site procedure manual and stored in the IAD study diary.

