#### IAD Care Assessment

The study nurses together with the ward nurses will collect the information needed to calculate the material cost based on product utilization, application frequency and days of treatment in the IAD study diary. On a daily basis the nurses will track the following information for each day stayed in the hospital during the study participation (day & night): incontinence status continued/discontinued, presence of urinary catheter or fecal management system, number of absorbent pad or diaper changes, number of intimate cleansing procedures, number of applications regarding Cavilon Advanced Skin Protectant or local IAD care products and number of IAD related visits of specialists. In addition, the IAD care products will be specified in more detail in the eCRF providing information such as product name, treatment duration period, product type, manufacturer, REF number (indicates the manufacturer's catalogue number so that the medical device can be identified), packaging unit, number of containments used for the study. The study nurses will receive a training how to document the information at the start of the study.

 
3M Deutschland GmbH [name] [name], Germany
	
Clinical Investigational Plan / Protocol
 
3M Confidential
	
CLIN-PROT-EU-05-293312 Version: 3 Status: Release Release Date: 01/30/2018 07:29:52 AM CST Page 40 of 60

--	--	---

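### Endpoint 9 (nursing time) has no stated unit, and minutes for one product application around Day 04 do not measure application workload when the arms apply at different intervals

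*Combined protocol and SAP*

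**What the plan says.** Section 7.3 lists endpoint 9 as "Nursing time to clean up incontinence and to administer IAD treatment products". It does not say whether this means per procedure, per day or per stay. Section 11.1 gives two parameters under nursing time: "Time taken to clean up incontinence in minutes", and the time spent applying the barrier product together with anything needed to prepare the skin for it.

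Section 11.2 says that these times "will be measured with a stopwatch at Day 04 (+/- 1 day", preferably when feces are present. The stopwatch instructions there start and stop around one clean-up, back and front, and one application to the study area. Section 7.4 (Day 02 – Day 20, item 3) gives the same step as "Day 04 IAD Nursing Time: Measure the time taken to clean up incontinence (front/back) and the time taken to administer the IAD treatment products", without the one-day window. Both flowcharts in Appendix 24.1 mark it at D04 only.

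On frequency, section 8.1 states that "Cavilon Advanced Skin Protectant will be applied every 72 hours in this study", and section 8.2 allows at most 7 applications in 21 days. Comparator products follow each hospital's own interval (section 8.1), which differs between products according to the footnote to Appendix 24.1 B. Under IAD Care Assessment in section 11.2, nurses record daily the "number of intimate cleansing procedures, number of applications regarding Cavilon Advanced Skin Protectant or local IAD care products". The stated purpose is material cost. No section combines these counts with the timed minutes. Section 6.1 plans descriptive summaries. Section 6.8 promises a separate SAP before data lock, which is not part of the text reviewed.

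**The concern.** The arms differ by design in how often product is applied. Day 04 is a scheduled device application day, and such a day comes only once in three. A time taken for one application on that day leaves out how often the application recurs, and that is what determines how much nursing time the regimen uses. A product that takes longer each time but is needed less often could look more expensive in nursing time than it is.

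The study has no hypothesis test to distort. Its stated purpose is to learn effect sizes and to judge whether a confirmatory trial is feasible (sections 5.1 and 6.2). An effect size for nursing time in the wrong unit would carry over into that planning.

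**Working it through.** **The plan's own figure.** Applications at a 3-day step from Day 01 fall on Days 1, 4, 7, 10, 13, 16 and 19. That is 7, which matches section 8.2 and Appendix 24.1 A. The device rate is therefore 7/21 = 1/3 application per day.

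**Inputs**
- Device rate: 1/3 per day (sections 8.1 and 8.2).
- Comparator rate k per day: not given; assumed over a range.
- Minutes per application, t_D (device) and t_C (comparator): not given; assumed. Write r = t_D/t_C.

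**Formula.** Daily application time is t_D/3 in the device arm and t_C × k in the comparator arm. Their ratio is (t_D/3)/(t_C × k) = r/(3k), so the arms break even at r = 3k.

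| Comparator applications per day, k | Break-even r = 3k |
|---|---|
| 1/3 (every 72 h) | 1 |
| 0.5 | 1.5 |
| 1 | 3 |
| 2 | 6 |
| 3 | 9 |
| 4 | 12 |
| 6 | 18 |

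**Reading the result for k > 1/3**
- 1 < r < 3k: the per-application figure favours the comparator, and daily application time favours the device.
- r < 1: both favour the device, but the per-application figure understates the saving.
- r > 3k: both favour the comparator, but the per-application figure overstates the device's disadvantage.

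At k = 1/3 the two ratios are equal. Below 1/3 the distortion would run the other way, in favour of the device.

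**Illustration (assumed minutes: device 3, comparator 2, so r = 1.5).** Per application the device is 3 − 2 = 1 minute slower. Per day it takes 3/3 = 1.0 minute.

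| k | Comparator min/day (2 × k) | Device min/day | Over 21 days, device (7 × 3) against comparator (21 × k × 2) |
|---|---|---|---|
| 1/3 | 0.67 | 1.0 | 21 against 14 min |
| 1 | 2 | 1.0 | 21 against 42 min |
| 2 | 4 | 1.0 | 21 against 84 min |
| 4 | 8 | 1.0 | 21 against 168 min |

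The sign reverses at k = 1, 2 and 4, and does not at k = 1/3. With a slower device application (assumed 5 against 2 minutes), the device takes 5/3 = 1.67 minutes per day against 2 at k = 1, so the reversal remains but is small.

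**Clean-up.** Appendix 24.1 schedules skin cleansing every day in both arms, and nothing ties the number of cleansings to the 72-hour interval. The factor 3k therefore does not apply to clean-up time. Cleansing counts may still differ between arms, and the diary records them.

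**Averaging window.** Under section 9.6 a healed patient who is still incontinent stays in the study. The device continues, but comparator application lapses where the hospital does not routinely use prevention products. Suppose, as an assumption, that k = 2 for the first 7 days and 0 afterwards. Over 21 days the mean is (2 × 7)/21 = 0.67, and the break-even r is 3 × 0.67 = 2 instead of 6. The window must therefore be fixed in advance.

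**The case against.** A reader might infer that the plan compares nursing time per procedure and that endpoint 9 will point the wrong way. The documents do not support that. No section says that the arms are compared per procedure; this is inferred from the parameter definitions and the single timing. Section 11.1 lists measurements, not the between-arm summary, and the SAP could still define a daily total. The reversal needs a device application that is slower than the comparator's and a k large enough for r < 3k. Neither is documented. Comparator care may be a wound dressing (Appendix 24.1 B), so a low k is possible. Clean-up, the other half of the endpoint, is outside the mechanism.

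Frequency is also not lost. Endpoint 7 covers frequency of application, and endpoint 8 covers resource use, which section 11.1 takes to include how many interventions were made. A careful reader could set these beside the timed minutes.

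The derived variable has weaknesses of its own: it extends one timed episode to every day, and that episode is preferably one with feces present.

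All of this stands, and it limits the claim. It does not remove it. As written, the protocol defines nursing time only in minutes per episode, leaves the unit of endpoint 9 open, and never brings the two arms' different application rates into that endpoint.

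**Conclusion.** The point holds for application time. Minutes for one application around Day 04 do not measure application workload unless the comparator is also applied every 72 hours. The size is the factor 3k: with a comparator used once a day, the per-application ratio overstates the device's relative daily application time threefold; at 4 times a day, twelvefold. Whether the direction also changes depends on r and k, which the documents do not give, so a reversal is possible but not established. The argument assumes that one timed application represents the others and that the 72-hour schedule is kept.

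This is one of eleven unranked endpoints in an exploratory study with no hypothesis and no pass/fail criterion. It affects how one effect size is read, not the sample size or error rates. The inputs for a better variable are already collected.

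**What to change.** In the SAP, before data lock, state the unit of endpoint 9 and add one derived variable:

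nursing minutes per patient-day = (timed application minutes × diary applications per day) + (timed clean-up minutes × diary cleansings per day).

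- Report the two components separately and combined, by arm and IAD stratum, with the arm difference and a descriptive 95% CI. Keep the per-procedure minutes beside them.
- Fix the averaging window: for example, days until first healing, with all days on study as a second summary.
- State the limitations. One timed episode represents all days. Clean-up is timed preferably with feces present, so it may overstate urine-only cleansings. Application is timed on the study area only, while the diary counts are not restricted to it.
- Reconcile the plain Day 04 in section 7.4 with the window of one day either side in section 11.2, so that the timing falls on an actual application.

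This is a cheap improvement: a few SAP lines and one derived variable, with no new data collection. The downside is that the result relies on these extrapolation assumptions.
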